#### **6.8. Demographic and Baseline Characteristics**

The Demographic and Baseline table of the double-blind treatment phase will be repeated for the ITTv5-OL, ITT-OL, and PPv5-OL populations and will be extended by the Baseline-OL values of weight, creatinine clearance, MMSE, and CDR.

The subject data listing of the double-blind treatment phase will be extended by the Baseline-OL values.

No formal statistical comparisons of treatment groups for any Baseline characteristics will be performed.

#### **6.9. Prior and Concomitant Medications**

Any medication that has been discontinued before the intake of the first dose of the open-label treatment phase study drug will be defined as prior medication. Any medication that was taken at the day of the first dose of the open-label treatment phase study drug or after will be defined as concomitant medication. Prior used medications and concomitant medications will be coded using the 01 March 2017 version of the WHO drug dictionary and the ATC level 1 term, ATC level 3 term, and PT will be presented in the analysis.

Data conventions are as described in Section 5.8.

The subject data listing of prior medications, and concomitant medications of the double-blind treatment phase will be updated, and the records of the open-label treatment phase medications will be added. An additional flag will be added to indicate the concomitant medications of the open-label treatment phase. A subset of this subject data listing will also be provided for subjects who were using

Sponsor:	TauRx Therapeutics Ltd.		
Protocol:	TRx-237-039		
Document Version No.:	3.0	Document Date:	07-JUN-2023

an antipsychotic treatment (during the double-blind or open-label treatment phase, see Section 12.4), including the reasons for use.

The following summaries/tabulations will be prepared for the ITTv5-OL and ITT-OL populations.

Tabulations with frequency and percentage, by treatment history and for the pooled treatment histories, will be prepared separately for all prior, for all concomitantly used drugs, and for all concomitantly used drugs that the patient is on at the time of the first dose of the open-label treatment phase study drug. Subjects reporting more than one medication are counted only once within each level summation.

Summary tables will be provided, showing the numbers of subjects with initiated treatments of SSRI/SNRI (see Section 12.4), drugs of serotonergic potential (see latest version of the Serotonergic Drugs List, Section 5.8), and any antipsychotic medications. For antipsychotics initiated on-treatment, the reasons for use will be also summarized.

#### 6.10. Secondary Efficacy Endpoint Analysis

The goal of the open-label phase is to demonstrate disease modification by comparing the ADAS-cog11 change from Baseline-OL at Week 104 between early and later starters using a non-inferiority margin. According to the study protocol the non-inferiority margin will be set to 2 units, based on the estimated treatment effect of  $5.2 \pm 1.3$  (mean  $\pm$  standard error) units from a pooled analysis of the studies TRx-237-005 / TRx-237-015.

This non-inferiority margin, and the thresholds mentioned in Section 6.11, have been selected based on the results of the two previous phase 3 studies TRx-237-005, and TRx-237-015. It was planned to change the non-inferiority margin to 50% of the observed 52 treatment effect, should the decline and treatment effect for this study, seen after topline and full analysis of the double-blind treatment phase, deviate strongly from the expectations based on the TRx-237-005/TRx-237-015 results. With the knowledge of the double-blind treatment phase results, the non-inferiority margin will be as selected, based on the two previous phase 3 studies TRx-237-005, and TRx-237-015.

Efficacy analyses will be conducted using the PPv5-OL population (see Section 3.1.2) with no imputation of missing values. Upscaling for the scales will be performed. The ITTv5-OL population will be analyzed as a supplementary analysis and will include only those subjects with at least one post-Baseline-OL value.

The key secondary endpoint is the Baseline-OL adjusted decline in ADAS-cog11 from Baseline-OL at Week 104. Repeated measures on this endpoint scheduled at Week 78, and Week 104 will be treated using a mixed effects model. Suppose  $\mu_{\text{early}}$  and  $\mu_{\text{late}}$  are the corresponding means of decline at Week 104 for the early and late starters, then the null and alternative hypothesis can be written as:

$$H_0: \mu_{\text{early}} - \mu_{\text{late}} \geq 2; \text{ versus}$$

Sponsor:	TauRx Therapeutics Ltd.		
Protocol:	TRx-237-039		
Document Version No.:	3.0	Document Date:	07-JUN-2023

$H_1: \mu_{\text{early}} - \mu_{\text{late}} < 2$ .

The analyses will be performed using the restricted maximum likelihood-based MMRM, including the randomization stratification variables (see Section 2.6) as fixed factors, the ADAS-cog11 Baseline-OL value as covariate, and the interaction term between early/ late starters (HMTM treatment history) indicator and visit; with an unstructured covariance matrix and the Kenward and Roger method of calculating the denominator degrees of freedom for the tests of fixed effects. According to the hypotheses, this is a lower-tailed test which will be performed at the alpha=0.025 level of significance.

Sample SAS code (will be fully validated at the analysis stage):

```

PROC MIXED DATA=dataset METHOD=REML COVTEST;
  CLASS subject treatmenthist(REF='Late') visit severity region prioruse;
  MODEL scorediff = treatmenthist/visit severity region prioruse scorew52 / SOLUTION CL
  DDFM=kenwardroger;
  REPEATED visit / SUB=subject TYPE=UN;
  LSMEANS treatmenthist*visit visit / CL;
  LSMESTIMATE treatmenthist*visit "intervention effect at Week 104" 0 1 0 -1 / CL testvalue=2
  LOWER ALPHA=.025;
  *Summary statistics for treatment difference based on LSM
  LSMESTIMATE treatment*visit "intervention effect at Week 78" 1 0 -1 0 / CL testvalue=2 LOWER
  ALPHA=.025;
  RUN;

```

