## **6. STATISTICAL ANALYSIS OF OPEN-LABEL TREATMENT PHASE**

### **6.1. Introduction**

The rationale of a delayed-start design is that, when the active drug has a purely symptomatic effect and has no effect on neuropathologic process, a delay in administration should have no lasting effect on subjects (null hypothesis). An effect that slows the progression of disease by modifying the underlying biological pathology, rather than only attenuating symptoms, would be evident if late starters fail to “catch up” to early starters. Demonstrating a disease-modifying effect would imply a sustained benefit of starting such drugs early. Throughout (that is, both the controlled and delayed-start phases), all subjects and study personnel on-site are blinded to each subject’s randomization to the early-start or late-start treatment group (HMTM treatment history).

Only subjects completing the 52-week double-blind treatment phase on- or off-treatment are eligible to enter the open-label treatment phase. This includes subjects, that have been randomized under a protocol version before version 5 and includes subjects who re-consented on a protocol version 5+ after the randomization and who completed the 52-week double-blind treatment phase. Subjects who have been off-treatment at Week 52 (TOTOS) stay off-treatment and do not receive any open-label treatment phase study drug.

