### **6.2. Open-Label Treatment Phase Definitions**

Based on the HMTM treatment history during the double-blind treatment phase “late” starters are defined as subjects originally randomized to control, and “early” starters are defined as subjects originally randomized to HMTM 16 mg/day or HMTM 8 mg/day. The last available assessment – for the scales: the last available (upscaled) value – prior to or on the same day of the start of the open-label treatment (Visit 7, Week 52) will serve as the Baseline assessment of the open-label treatment phase (Baseline-OL). A delayed performed Week 52 MRI assessment will be eligible for the Baseline-OL assessment if it has been done within 14 days after starting the open-label treatment phase.

The treatment group of subjects originally randomized to control will be labeled as “MTC 8 mg/week”.

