#### 6.10.1. Sensitivity Analysis

The subgroups of subjects originally randomized to HMTM 16 mg/day and 8 mg/day will be analyzed separately, as described in Section 6.10.

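### SAP 6.10 lets a delayed-start pass count as disease modification without requiring any Week 52 benefit; at the planning SD an inert drug would pass about 84–86% of the time

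*SAP*

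**What the plan says.** SAP 6.1 gives the rationale. A purely symptomatic drug leaves no lasting trace of a delay in starting, whereas slowing of the disease "by modifying the underlying biological pathology, rather than only attenuating symptoms, would be evident if late starters fail to" catch up with early starters.

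SAP 6.10 turns this into a test on the ADAS-cog11 "change from Baseline-OL at Week 104 between early and later starters using a non-inferiority margin". H0 is early minus late of 2 units or more, H1 is less than 2, and "this is a lower-tailed test which will be performed at the alpha=0.025 level of significance". The model has the "Baseline-OL value as covariate, and the interaction term between early/ late starters (HMTM treatment history) indicator and visit". The primary population is PPv5-OL, with ITTv5-OL as supplementary.

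Under SAP 6.2, early "starters are defined as subjects originally randomized to HMTM 16 mg/day or HMTM 8 mg/day", so the main test pools both doses. Under SAP 6.10.1, those "originally randomized to HMTM 16 mg/day and 8 mg/day will be analyzed separately" as a sensitivity analysis.

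On the margin, SAP 6.10 records: "It was planned to change the non-inferiority margin to 50% of the observed 52 treatment effect", should results deviate strongly from expectation. It then says: "With the knowledge of the double-blind treatment phase results, the non-inferiority margin will be as selected", that is, 2 units.

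SAP 6.4, protocol 17.2 and the protocol synopsis put open-label entry at 160–170 per arm and the power of this comparison at about 80%.

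**The concern.** The catch-up argument needs a Week 52 gap to start from. The test begins at Week 52 and asks only whether early starters then decline no more than 2 units faster than late starters. If the drug does nothing, both groups decline in parallel, the true difference is 0, and 0 lies inside H1. The formal rule therefore puts a drug with no effect on the side that SAP 6.10 describes as demonstrating disease modification.

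No other rule closes this:
- SAP 5.2 covers only the co-primaries and the order of populations.
- The secondary sequence in SAP 5.9.3 does not contain the delayed-start test.
- Protocol 17.9 makes only the full double-blind analyses and the interim report depend on rejecting the primary nulls.
- Protocol 17.4.7 makes several dose-response analyses contingent on significant results, so conditioning was available, but it is not applied here.
- The displays from the Visit 2 Baseline to Week 104 (protocol 17.4.6, SAP 6.12) would show whether a gap exists but carry no success criterion.

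What is at stake is the key secondary claim. Disease modification could be stated when there was no Week 52 effect to preserve.

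**Working it through.** **Inputs from the documents.** Margin 2 and one-sided alpha 0.025 (SAP 6.10); SD 5.9 for 52-week ADAS-cog11 change and 20–25% withdrawal (SAP 5.3); a further 10% dropout in the open-label phase (SAP 6.4); 200, 50 and 200 randomized to 16 mg, 8 mg and control (protocol 17.2).

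**Assumptions not in the documents.** SD 5.9 also holds for Weeks 52–104; the 8 mg arm drops out at the same rates; no per-protocol loss unless stated.

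**Entrants.** 200 × 0.75 = 150 and 200 × 0.80 = 160, not 160–170 (which would imply 15–20% dropout). After a further 10%: 135–144 per main arm. Pooled early starters: 250 × 0.75 × 0.9 = 168.75 and 250 × 0.80 × 0.9 = 180. As a check, the 96.7% and 93.2% powers in SAP 5.3 reproduce with a t-test at 150 per arm.

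**Formula.** P(pass) = Φ((2 − true difference)/SE − 1.96), with SE = 5.9 × √(1/n_early + 1/n_late).

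**The plan's own figure, true difference 0, equal arms.**
- 135 per arm: SE 0.718; 2/0.718 = 2.785; Φ(0.825) = 79.5%.
- 144 per arm: SE 0.695; 2/0.695 = 2.876; Φ(0.916) = 82.0%.

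This reproduces the stated power of about 80%, and only at a true difference of 0. That power is therefore also an inert drug's chance of passing.

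**The planned pooled test, inert drug.**
- 168.75 vs 135: SE 0.681; Φ(2.936 − 1.96) = 83.5%.
- 180 vs 144: SE 0.660; Φ(3.032 − 1.96) = 85.8%.

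**Sensitivity, inert drug.** With an assumed further 10% loss to PPv5-OL, the pooled rate is 79.5–82.0%. Over SD 5 to 8 and all four size combinations, the range is 53.7% (SD 8, 135 per arm) to 94.7% (SD 5, 180 vs 144).

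**Gating on a favourable Week 52 ADAS-cog11 result (two-sided 0.05).** For an inert drug, the chance of meeting both conditions cannot exceed 2.5%. If the two estimates are independent it is 0.025 × 0.835 to 0.025 × 0.858, or 2.1%.

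**What the gate leaves open.** Suppose a purely symptomatic Week 52 gap g is fully closed by Week 104. The true difference is then g. Taking the gap as equal in the 16 mg and pooled groups, with SD 5.9, independence and no dependence of later change on the Week 52 score:

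| g | pooled test passes | Week 52 gate passes (150–160 per arm) | both |
|---|---|---|---|
| 1.0 | 31.1–32.9% | 31.0–32.7% | 9.6–10.7% |
| 1.5 | 11.0–11.5% | 59.3–62.1% | 6.5–7.1% |
| 2.0 | 2.5% | 83.3–85.6% | 2.1% |

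The middle rows exceed 2.5% because the fixed margin is larger than the gap itself.

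**Power cost of the gate.** For a fully retained effect the true difference is again 0. For 2.6 units the loss is at most 1 − 0.967 = 3.3 points, whatever the correlation. Under independence, the pooled 83.5–85.8% becomes 80.8–83.7% (2.6 units), 69.6–73.5% (2.0), 49.5–53.3% (1.5) and 25.9–28.1% (1.0).

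**The case against.** The strongest reply is that the design is aimed at a symptomatic drug whose late starters catch up, not at an inert one. Against a caught-up effect of 2 units or more the test does hold its level, at 2.5% or less. Readers will also see the Week 52 result and the displays from the Visit 2 Baseline. Both statements are true, but neither supplies a rule, and SAP 1.1 sends the planned analyses into submissions and manuscripts.

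Several criticisms of the remedy stand. The gate uses 16 mg/day vs control in E-MITTv5, while the test pools both doses in PPv5-OL, so a significant gate does not prove a gap in the people tested. It leaves the fixed margin alone, hence the 6.5–11% in the table. SAP 3.0 was written after the double-blind unblinding, so the gate's outcome is already known and it cannot be prospective error control. Absence from the SAP 5.9.3 sequence carries little weight, because section 5 covers only the double-blind phase.

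A reader might infer that the sponsor discarded the 50% margin rule because of the results. The documents do not show that. The rule applied only if results deviated strongly from expectation, that phrase is not defined, and keeping 2 units fits equally well with a trigger that was not met.

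A reader might also call 84–86% a type I error rate. It is not one for the stated H0, since a difference of 0 lies in H1. The gap is between the hypothesis tested and the conclusion attached to it.

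**Conclusion.** The point holds. As written, passing the delayed-start test is treated as showing disease modification whether or not there was a Week 52 effect. An inert drug passes the pooled test about 84–86% of the time if SD 5.9 carries over to Weeks 52–104 and there is no per-protocol loss, and about 80–82% with a further assumed 10% loss. No Week 52–104 SD is given, so the 54–95% range should be read with these figures. The conclusion does not depend on the exact value, because the stated power is itself computed at no difference.

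The finding does not reach the co-primary decision: SAP 5.2 still requires both endpoints before HMTM is called superior. The entrant range is a separate arithmetic slip; the stated power of about 80% survives it.

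**What to change.** 1. Add to SAP 6.10: *Rejection of H0 will be interpreted as evidence of disease modification only if the Week 52 ADAS-cog11 comparison of HMTM 16 mg/day versus control (E-MITTv5) is significant at two-sided 0.05 in favour of HMTM; otherwise the estimate and confidence interval are reported without that conclusion.* Report alongside it the Week 52 difference for the pooled early starters actually tested.
2. List this in SAP section 10 as an interpretation rule added after the double-blind unblinding. It can only withhold a claim. State its limits there: at most 2.5% for an inert drug, but about 6.5–11% for a fully caught-up symptomatic effect of 1.0–1.5 units under the assumptions above.
3. In SAP 6.4, protocol 17.2 and the synopsis, restate open-label entrants as 150–160 per arm (135–144 after the further 10% dropout).

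The cost is a short addition to SAP 6.10, an entry in section 10, one extra reported Week 52 contrast from data already collected, and a corrected range in three places. The power cost is at most about 3 points for a fully retained 2.6-unit effect and larger for smaller effects.

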#### **17.4.6 Open-Label, Delayed-Start Analysis**

“Late” starters, *i.e.*, subjects originally randomized to placebo, will be compared to “early” starters, *i.e.*, those originally randomized to LMTM 16 mg/day or 8 mg/day (pooled, and individually for both groups as a sensitivity analysis). The last assessment prior to start of open-label treatment (pre-dose at Visit 7) will serve as the baseline assessment for these comparisons. The analyses will be based on a similar linear mixed model for repeated measures as outlined for the FDA/EMA primary analysis (see model specification in Sections 17.4.2 and 17.4.3) with the aim to investigate whether there is a difference in change in primary and MRI imaging endpoints dependent on LMTM treatment history (certain covariates in the model might be dropped if the model does not converge; see SAP for details).

The comparison will be implemented through a non-inferiority test. The non-inferiority margin for the primary endpoint of ADAS-cog11 will be 2 units, motivated by the fact that these 2 units are small compared to the estimated treatment effect of > 5 units (~40% of this effect size). Margins for other endpoints which are exploratory to support a disease modifying argument will be defined in the SAP.

The results will also be presented with the Visit 2 Baseline as baseline, and treatment visits Week 26 and Week 52 in the open-label, delayed-start phase as Week 78 and Week 104.

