treatment indicator and the interaction term between treatment and visit, the randomization stratification variables (see Section 2.6) as fixed factors, and the respective efficacy Baseline/Baseline-OL value as covariate; with an unstructured covariance matrix and the Kenward and Roger method of calculating the denominator degrees of freedom for the tests of fixed effects. One version of the line graph will include/present the visits from Baseline to Week 104, including Baseline as the covariate in the model, and a second version will include/present the visits from Baseline-OL to Week 104, including Baseline-OL as the covariate in the model. This will be repeated for the verified AD diagnosis subgroups MCI-AD and probable AD.

Based on the ITTv5-OL population, the following pairwise correlations will be analyzed by means of scatter plots with symbolized treatment groups, which include both the parametric Pearson correlation coefficient and the non-parametric Spearman's rank correlation coefficient and their corresponding p-values for each treatment group, along with the regression lines:

- (Changes from Baseline): MRI whole brain volume at Week 52 vs. ADAS-cog11 at Week 104
- (Changes from Baseline): MRI whole brain volume at Week 52 vs. ADCS-ADL23 at Week 104
- (Changes from Baseline): MRI whole brain volume at Week 52 vs. CDR-SOB at Week 104
- (Changes from Baseline): MRI whole brain volume at Week 52 vs. MMSE at Week 104

Based on the ITTv5 population, for ADAS-cog13, ADAS-cog11, ADCS-ADL23, and the two MRI parameters whole brain volume and temporoparietal lobe volume, the observed change from Baseline at Weeks 26, 52, 78, and 104 will be analyzed with a paired t-test, separately for the subjects originally randomized to HMTM 16 mg/day and subjects originally randomized to MTC 8 mg/week. Two-sample t-test comparisons between the treatment groups for the respective endpoints and each of the Weeks 26, 52, 78, and 104 will be presented as well. This will be repeated for the verified AD diagnosis subgroups MCI-AD and probable AD.

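### The delayed-start test adjusts for the Week 52 ADAS-cog11 score, which treatment may already have changed, so its 2.5% level is not protected for the randomized early-late difference; the direction of the error is unknown

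*SAP*

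**What the plan says.** SAP 6.2 takes as Baseline-OL the last ADAS-cog11 value on or before the day open-label treatment starts (Visit 7, Week 52). SAP 6.10 then defines the endpoint: "The key secondary endpoint is the Baseline-OL adjusted decline in ADAS-cog 11 from Baseline-OL at Week 104". The hypotheses are written in terms of μ_early and μ_late, which "are the corresponding means of decline at Week 104 for the early and late starters". H0 is μ_early − μ_late ≥ 2. On the margin, "According to the study protocol the non-inferiority margin will be set to 2 units"; on the level, "this is a lower-tailed test which will be performed at the alpha=0.025 level of significance".

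The sample code fits "MODEL scorediff = treatmenthist/visit severity region prioruse scorew52", so one slope on the Week 52 score applies to both groups and to both Weeks 78 and 104. Early starters are the 16 mg and 8 mg arms pooled, and the main population is PPv5-OL.

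Other analyses from the original baseline are planned, but none is a non-inferiority test. Protocol 17.4.6 says: "The results will also be presented with the Visit 2 Baseline as baseline". SAP 6.12, labelled post hoc, says: "One version of the line graph will include/present the visits from Baseline to Week 104, including Baseline as the covariate in the model". SAP 6.10.1 only splits the early starters by dose, and the ITTv5-OL analysis only changes the population.

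**The concern.** SAP 6.1 rests the disease-modification argument on randomized history: if late starters fail to catch up, the early benefit was lasting. That needs the difference in Week 52 to 104 change between the groups as randomized. The fitted model instead compares early and late starters who have the same Week 52 score. If the drug lowered that score, an early and a late starter who match at Week 52 are not alike in other respects; the early starter would have scored worse without treatment. The contrast then contains a term that comes from the first-year drug effect and not from what happened in the second year.

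At stake is the trial's only formal delayed-start test. The error can go either way: a disease-modification claim when late starters are in fact catching up by the margin, or a missed claim when the early benefit persists. SAP 6.11 repeats the model for ADCS-ADL23 and the MRI volumes.

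**Working it through.** **Inputs from the documents.** Margin 2 and one-sided 0.025 (SAP 6.10). SD of 52-week ADAS-cog11 change 5.9, design effect 2.6, prior-study effect 5.2 (SAP 5.3). Arms of 200, 50 and 200; withdrawal 20% to 25%, then a further 10% (SAP 5.3, 6.4). Stated power about 80% (SAP 6.4).

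**Assumed, because not given.** SD 5.9 for the Week 52 to 104 change; b from -0.20 to +0.20.

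**1. Reproduce the stated power.** Power = Φ(2/SE − 1.96) at a true difference of 0.
- 200 × 0.75 × 0.90 = 135 per arm: SE = 5.9 × √(2/135) = 0.718, power 79.5%. This matches.
- 160 × 0.90 = 144 per arm gives 82.0%; 170 × 0.90 = 153 gives 84.3%. (The stated 160 to 170 entrants do not follow from 20% to 25% withdrawal of 200, which leaves 160 to 150.)
- Pooled early group: 250 × 0.80 × 0.90 = 180 against 200 × 0.80 × 0.90 = 144. SE = 5.9 × √(1/144 + 1/180) = 0.66, power 85.8%. The steps below use this case.

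**2. What the model estimates.** Let D be the early-minus-late difference in Week 52 to 104 change. The early group's mean Week 52 score is lower by δ. The adjusted contrast is

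D − b × (−δ) = D + b × δ.

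**3. Rejection rate at D = 2**, from Φ(−b × δ/SE − 1.96):

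| b | δ = 2.6 | δ = 5.2 |
|---|---|---|
| -0.20 | 12.1% | 35.1% |
| -0.10 | 5.9% | 12.1% |
| -0.05 | 3.9% | 5.9% |
| 0 | 2.5% | 2.5% |
| +0.05 | 1.6% | 0.9% |
| +0.10 | 0.9% | 0.3% |

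Example: b = -0.20 and δ = 2.6 give 0.52/0.66 = 0.79, and Φ(0.79 − 1.96) = 12.1%.

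**4. Power at D = 0 and δ = 2.6**, from Φ((2 − b × δ)/SE − 1.96): 96.9% at b = -0.20, 92.9% at -0.10, 85.8% at 0, 75.1% at +0.10.

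**5. Why the sign of b is open.** Suppose the true Week 52 severity has SD σT, visit error has SD σe, and later change rises by g per unit of true severity. Then b = (g σT² − σe²)/(σT² + σe²). Error alone (g = 0) makes b negative: σT = 7 and σe = 2.5 give -0.113; 6 and 3.0 give -0.20; 7 and 1.5 give -0.044. If sicker subjects decline faster, b rises: with 7 and 2.5, g = 0.127 gives 0 and g = 0.25 gives +0.109. All of these values are assumptions.

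**6. Simulation check.** 4,000 trials per cell, 144 against 180, severity strata 2:3:1, with complete-data ANCOVA at Week 104 in place of the MMRM. At D = 2 and δ = 2.6 the planned adjustment rejects 12.2% (b = -0.20), 6.6% (-0.113), 3.7% (-0.044), 2.4% (0) and 0.65% (+0.109). At D = 0 its power runs from 97% (b = -0.20) to 71% (b = +0.109). With no Week 52 covariate, or with the Visit 2 score instead, the rate at D = 2 is 1.9% to 2.9% for every δ (0, 2.0, 2.6, 5.2) and b tried, and power is 84% to 88%.

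**The case against.** **The SAP names an adjusted endpoint.** SAP 6.10 calls the endpoint Baseline-OL adjusted, in the same style as the co-primaries. For that conditional contrast the test keeps its level if the model is right. This stands. The criticism concerns which quantity is tested; it does not claim that the code contradicts the stated endpoint.

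**The direction is not established.** This also stands. With b = 0 the level is 2.5% whatever the drug does, and with b > 0 the test is conservative. An unknown b is, however, a reason to prefer a test that does not depend on it.

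**False passes need catch-up.** They require a true difference of at least 2. If the drug is disease-modifying and D is near 0, H0 is false and only power moves. This stands.

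**Visit 2 results will be shown.** Protocol 17.4.6 and SAP 6.12 will show whether the gap persists from the original baseline. That helps a reader, but the SAP 6.12 output covers only 16 mg against control in ITTv5-OL, is post hoc, and is not tested against the margin.

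**Changing the test has a price.** Protocol 17.4.6 takes Visit 7 as baseline in a model like the primary one, which carries the baseline as covariate (Protocol 17.4.2). SAP v3.0 also followed partial unblinding (SAP 6.12, 10). Both points stand and bear on how the fix is made.

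**Conclusion.** The concern holds in a limited form. The Week 52 covariate shifts the tested contrast by b × δ, so 2.5% is not protected for the randomized early-late difference when the drug changes Week 52 scores and later change depends on those scores. At D = 2 and δ = 2.6 the rate lies between about 0.9% and 12% for b from +0.10 to -0.20. The algebra is firm. The size rests on an assumed b and on SD 5.9 for the second year, and the calculations ignore missing data and PPv5-OL selection.

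Two stronger readings are tempting, and the documents support neither:
- *The test exceeds its error rate whenever the drug works.* A drug effect is necessary but not sufficient; b must also be negative and the true difference must be at least 2.
- *A purely symptomatic drug of the design size would often pass.* With full catch-up D = δ. At δ = 2.6 and b = -0.20 the contrast is 2.6 − 0.52 = 2.08, still above the margin, and the pass rate is 1.9%. The exposed cases are full catch-up with δ near 2 (4.9% at b = -0.10 and 8.8% at b = -0.20) and partial catch-up of about 2 units from a larger effect.

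**What to change.** In SAP 6.10, for pooled early starters in PPv5-OL, test [early minus late at Week 104] minus [early minus late at Week 52] against 2 at one-sided 0.025. Either of two models will serve:
- an MMRM over Weeks 13, 26, 39, 52, 78 and 104 with the Visit 2 Baseline as covariate, with contrast coefficients early 0 0 0 -1 0 1 and late 0 0 0 1 0 -1;
- the planned model of Week 52 to 104 change with the Week 52 covariate removed.

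With an additive Visit 2 term and complete data, the covariate cancels from the first contrast. The simulation used an ANCOVA of the change and not the six-visit model, so the chosen form should be checked before use. Keep the Week 52-adjusted model as a sensitivity analysis, and make the same change in SAP 6.11.

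If the sponsor will not replace the key-secondary model after partial unblinding, name this test as a sensitivity analysis in SAP 6.10.1 and require the disease-modification claim to be consistent with it.

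Cost: no new data and no material loss of precision, but some programming, since the SAP 6.12 model is not set up for the pooled early group in PPv5-OL. It is a departure from Protocol 17.4.6 made after double-blind unblinding, so the reason and date should be recorded before open-label database lock. It does not remove the selection that comes from restricting the comparison to subjects who completed Week 52.
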